#### **10.4.1.3 Data Listings**

Vital signs values will be listed by treatment and subject.

Subjects with any markedly abnormal changes at any time-point will be also listed with all values of the corresponding vital signs. The vital signs values with markedly abnormal changes will be flagged out.

#### **10.4.2 ECGs**

Baseline for all ECG analyses will be the values obtained at the last assessment prior to the first dose of IMP. End of trial will include the last post-baseline observation during the trial.

##### **10.4.2.1 Summary Statistics**

ECG qualitative data will be summarized in number (%) for “normal”, “abnormal – not clinically significant (NCS)” and “abnormal –clinically significant (CS)” collected in CRF.

##### **10.4.2.2 Markedly Abnormal Changes**

Not applicable since no quantitative data will be collected for this study.

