### 3 INVESTIGATIONAL PLAN

#### 3.1 Overall Trial Design

##### 3.1.1 Overall Design and Control Methods

This is a prospective, randomized, double-blind, placebo-controlled parallel trial in subjects with PWS between the ages of 10 and 18 years of age with genetically confirmed diagnosis of PWS and a documented nutritional phase 3 symptom criteria as defined by Miller et al 2011.[\[5\]](#) The trial includes a Screening Period, a 14-day Treatment Period, and a Follow-Up Period. Subjects, along with their parent/caregiver, will be required to visit the investigational site 4 times over the course of the trial, and participate in 2 phone call assessments.

- Visit 1: Screening Period (Day -7 to Day 0)
- Visit 2: Baseline 1st day dosing on site (Day 1)
- Visit 3: 2nd day dosing on site (Day 2)
- Phone call assessment (Day 8)
- Visit 4: End-of-Treatment Visit (Day 15)
- Follow-up phone call (Day 19±3)

Following appropriate informed consent procedures, subjects will undergo screening evaluations to determine eligibility before randomization. Screening evaluations include a physical examination, vital signs, height, weight, 12-lead electrocardiogram (ECG), nasal examination, and laboratory assessments - hematology, clinical chemistry, hemostasis, and urinalysis. Approximately 38 eligible male or female subjects will be randomized at Visit 2 to 1 of 2 treatment groups for 14 days:

- Carbetocin: each spray pump actuation will deliver a 50 µL volume of solution containing 1.6 mg carbetocin; each dose will consist of 3 spray pump actuations in each nostril to deliver a total of 9.6 mg carbetocin
- Placebo: each spray pump actuation will deliver a 50 µL volume of sterile sodium chloride solution 0.9%; each dose will consist of 3 spray pump actuations in each nostril

After randomization, efficacy measures and other assessments, including physical examination, vital signs, nasal examination, and collection of blood samples for clinical laboratory and pharmacokinetic (PK) evaluation, will be performed at selected visits according to [Table 1](#). Subjects will be closely monitored for adverse events throughout the trial following informed consent.

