#### 4.3 Restrictions

##### 4.3.1 Prior and Concomitant Therapies

Use of any concomitant therapy will be recorded in the medical source data and the eCRF by trial staff, following the subject interview at each visit. Required information includes the drug name, strength, formulation, route of administration, dosing frequency, indication for use, start and stop date, times. Any changes (including new therapies) must be recorded at each subsequent trial visit.

Prior and concomitant use of growth hormone is permitted.

Prior and concomitant use of the following types of medications is permitted only if the prescribed dosage of the medication has been stable for  $\geq$  6 months at time of screening:

- A single selective serotonin reuptake inhibitor (SSRI) or selective norepinephrine reuptake inhibitor (SNRI)
- An antipsychotic medication
- A wakefulness-promoting drug
- A thyroid hormone

The table below lists examples of some common SSRIs, SNRIs, antipsychotics, wake promoting agents, and hypothyroid medications.

Class of Drug	Examples of Common Drugs in each Class
SSRIs	Citalopram
	Sertraline
	Paroxetine
	Fluoxitene
SNRIs	Duloxetine
	Venlafaxine
	Desvenlafaxine
Antipsychotics	Respiridone
Wakefulness-promoting drugs	Amphetamine
	Modafinil (Provigil)
	Armodafinil (Nuvigil)
Thyroid hormones	Levothyroxine
	Lyothyronine

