**Table 1 Schedule of Activities**

Period:	Screening	Treatment					End of Treatment Visit / Early termination visit	F/U phone call
		Baseline			1-Week Assessment			
Visit:	1	2	3				4	
Days:	-7 to 0	1	2	3-7	8 (+/-1)	9-14	15	19 (+/-3)
IMP Dosing:	NA	On site	On site	Off site			On site	NA
Assessments								
Written informed consent and assent	X							
Inclusion/exclusion criteria	X							
Prior/concomitant medication	X	X	X		X		X	
Physical examination	X						X	
Nasal examination a	X	X	X				X	
Medical history	X							
Demographics	X							
Urine drug and alcohol screen	X						X	
Urine pregnancy test	X						X	
Height and Weight	X						X	
Vital signs b	X	X	X				X	
Electrocardiogram c	X	X	X				X	
Blood samples for clinical chemistry, hematology, hemostasis, and urinalysis	X		X				X	
Blood samples for pharmacokinetics d		X	X					
Nutritional phase assessment	X							
Randomization e		X e						
HPWSQ-R and HPWSQ-R-C	X	X			X		X	
CGI-S		X						
CGI-I					X		X	
CY-BOCS	X				X		X	
Food Domain of Reiss Profile	X				X		X	
IMP administration training		X						
Dispense IMP		X	X	X	X	X		
Return IMP							X	
IMP dosing		X	X	X	X	X		
Adverse events	X	X	X		X		X	X

CGI-I=Clinical Global Impression-Improvement after treatment; CGI-S=Clinical Global Impression-Severity; CY-BOCS= Children's Yale-Brown Obsessive-Compulsive scale; F/U=follow-up; HPWSQ-R=Hyperphagia in Prader-Willi Syndrome Questionnaire-Responsiveness; HPWSQ-R-C=Hyperphagia in Prader-Willi Syndrome Questionnaire-Clinician ; IMP=investigational medicinal product

- a Nasal examinations to be done at Visit 1 (anytime), within 1 hour prior to each dose at Visit 2 and Visit 3, and at Visit 4 (anytime).
- b Includes pulse, respiration rate, blood pressure and body temperature. At Visit 2 and 3, vital signs will be monitored prior to and after IMP dosing at 30-minute intervals for 2 hours after each dose.
- c ECG to be done within 1 hour after morning dose at Visit 2 and 3.
- d Three blood samples to be collected at Visit 2 and Visit 3, according to the schedule specified in section 7.2.6 Clinical Laboratory Tests/Pharmacokinetic Assessments. All PK labs are to be done prior to subsequent dose.
- e Randomization will be done within 24 hours prior to the Visit 2, morning dose.

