### 7.2.5 12-Lead Electrocardiogram

After at least a 5-minute rest in a supine position, a 12-lead ECG will be obtained at each visit (or at early termination). Additional ECGs may be obtained if clinically indicated.

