##### **Electrocardiograms**

Subjects with clinically significant deteriorations in ECG findings will be identified.

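### ECGs are kept only as three-level labels and never tabulated against baseline, so interval changes within a label cannot be shown or bounded; recording intervals and adding a shift table would be cheap

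*Combined protocol and SAP*

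**What the plan says.** **Collection.** Protocol Table 1 marks an ECG at Visits 1, 2, 3 and 4, and protocol 7.2.5 confirms a 12-lead recording at every visit, with extra ones if clinically indicated. A footnote to Table 1 fixes the timing on the two dosing days: "ECG to be done within 1 hour after morning dose at Visit 2 and 3". Neither place names an interval to be measured, a reader, or central reading.

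**Protocol analysis.** Section 9.8.4 has one sentence on ECGs: "Subjects with clinically significant deteriorations in ECG findings will be identified".

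**SAP analysis.** Section 10.4.2 defines baseline as the last assessment before the first dose. Section 10.4.2.1 then states: "ECG qualitative data will be summarized in number (%) for" three CRF categories (normal, abnormal not clinically significant, abnormal clinically significant). Section 10.4.2.2, on markedly abnormal changes, reads: "Not applicable since no quantitative data will be collected for this study". Section 10.4.2.3 adds a listing by treatment and subject. SAP Appendix 1 has numerical limits for laboratory tests and vital signs and none for ECGs.

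**The concern.** A 12-lead ECG yields continuous measurements, and here two of the four are tied to dosing. Reducing each to one of three labels discards any movement of PR, QRS or QTc that does not change the label. Two arms could differ in mean interval change and still produce identical ECG tables.

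The labels are also not used to the full. The SAP defines an ECG baseline, but no ECG table uses it. Counts by category show how many subjects are abnormal at a visit; they do not show how many moved from normal to abnormal, which is what a deterioration means.

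What is at stake is the quality of the descriptive safety record. The subjects are aged 10 to 18, and the earlier intranasal human trial described in protocol 3.5.4 was in healthy adults. Protocol 4.3.1 permits stable-dose concomitant drugs, among them "An antipsychotic medication" and an SSRI or SNRI. The documents report no ECG effect of carbetocin or of these drugs, so this is background to the request and not evidence of a risk.

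**Working it through.** **1. Number of ECGs.** One at each of Visits 1 to 4 gives 4 per completing subject. With about 38 randomized (protocol 3.2), 38 x 4 = 152. This is a maximum for scheduled ECGs, because about 20% dropout is assumed (protocol 9.1). Two of the four are within 1 hour after the morning dose. Interval values planned for the analysis data: none.

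**2. ECG set beside the other safety measures in the SAP.**

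| Measure | Change from baseline | Shift table | Numerical criteria |
|---|---|---|---|
| Laboratory (10.3) | yes | yes | Appendix 1 |
| Vital signs (10.4.1) | yes | no | Appendix 1, by age; pulse and blood pressure also by sex |
| Nasal grade (10.5.1) | not applicable, categorical | yes | not applicable |
| ECG (10.4.2) | no | no | none |

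The nasal grade is the closest comparison: it is also an ordered category, and the SAP already plans a shift table for it.

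**3. Which ECG is the baseline.** The Visit 2 ECG follows the dose. Unless an unscheduled pre-dose ECG exists, the last one before first dose is therefore the screening ECG (Day -7 to 0). There is no same-day pre-dose reference, so change from baseline within an arm mixes any drug effect with day-to-day and time-of-day variation. The placebo arm shares that mixture, which makes the between-arm comparison the informative one.

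**4. What recorded intervals could show (illustration).** The documents state no ECG precision figure to reproduce and give no SD for QTc change; 15 and 20 ms are assumed. Two-sided 95% half-width for the arm difference in mean change = t(0.975, 2n - 2) x SD x sqrt(2/n).

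- n = 19 per arm (all randomized): t(36 df) = 2.03 and sqrt(2/19) = 0.324. SD 15 gives 9.9 ms; SD 20 gives 13.2 ms.
- n = 15 per arm (30 completers; 38 x 0.80 = 30.4): t(28 df) = 2.05 and sqrt(2/15) = 0.365. SD 15 gives 11.2 ms; SD 20 gives 15.0 ms.

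The first line suits Days 1 and 2 and the second suits Day 15. Both are descriptive, since SAP 10.1 plans no formal safety testing.

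**The case against.** The strongest reply is that this is an open design choice in a small phase 2a trial. ECG is not named among the safety endpoints, no section promises interval analysis, and protocol 9.8.4 asks only that clinically significant deteriorations be identified. With about 38 subjects, someone reading the SAP 10.4.2.3 listing can follow each subject from the baseline label onward. Findings that the investigator judges clinically significant are also a source of adverse events (protocol 8.2.1), which are tabulated by arm. Prior concern is lowered too: cardiovascular disorders are excluded, protocol 1.3 reports no important safety concerns, and protocol 3.5.4 reports no safety signals up to the 9.6 mg dose used here. All of this stands, and it is why the point is an improvement and not a defect.

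A reader might go further and infer that the trial can detect no ECG effect at all. The documents do not support that. Abnormal but not clinically significant ECGs are counted, so a large rise in abnormality could show: for an assumed rise from 5% to 30%, power is roughly 79% with 19 per arm at one-sided 10% (normal approximation, rough at this size). Nor are the tracings necessarily lost. Protocol 10.1 defines source documents to include recorded instrument data and requires source records to be retained, so intervals could be measured later, although neither document plans it.

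Two further inferences lack a basis in the text. No section says who reads the ECGs, so variation between readers at the roughly 3 sites is possible but not stated. No section gives a reason for the post-dose timing, so an intention to catch an acute effect is a guess.

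**Conclusion.** The point holds in a limited form. From the planned data and tables, a change in PR, QRS or QTc that stays within a label category can be neither shown nor bounded. The comparison with baseline that protocol 9.8.4 implies appears in no ECG table and is left to listings and adverse-event reports.

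A reader might take SAP section 12, which declares no deviations from the protocol's analyses, to be contradicted by this. That goes too far: the listing and adverse-event reporting can still identify deteriorations, only less visibly than a table would.

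The counts rest on the documents: up to 152 scheduled ECGs and no planned interval values. The gain in precision, a half-width of about 10 to 13 ms with 19 per arm or 11 to 15 ms with 15 per arm, rests wholly on the assumed SD of 15 to 20 ms. This is a cheap improvement to descriptive safety data, not an error in a stated analysis.

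**What to change.** 1. **Shift table.** In SAP 10.4.2, add a table by arm of the three ECG categories, from baseline to worst post-baseline. State whether unscheduled ECGs count: SAP 10.1 leaves them out after baseline unless specified, while the laboratory shift tables include them. This uses data already collected and costs one table.

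2. **Intervals.** Add heart rate, PR, QRS, QT and QTc, with the correction formula named, to the eCRF for each scheduled ECG. Summarise values and change from baseline descriptively by arm and timepoint. State that baseline is normally the screening ECG and that the between-arm comparison is the one to read. Add ECG criteria to SAP Appendix 1, chosen by the sponsor and appropriate to age, as is already done there for vital signs. The documents supply no cut-offs, and none is proposed here. Replace the text of SAP 10.4.2.2 accordingly.

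The cost is five eCRF fields per ECG and a few tables, with no added ECG or visit. The drawbacks are the extra data entry and the lower precision of site-machine intervals compared with central reading.

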##### **10.4.2.3 Data Listings**

ECG data will be listed by treatment and subject.

#### **10.5 Other Safety Variables**

The remainder of the data collected in the CRF (e.g., pregnancy test, nasal examination) will be listed by treatment and subject. Nasal examination will be also summarized as described in the following section.

##### **10.5.1 Nasal examination**

Baseline for nasal examination analyses will be the values obtained at the last assessment prior to the first dose of IMP. End of trial will include the last post-baseline observation during the trial.

Number (%) of subjects with each grade of nasal examination result will be summarized by treatment, visit and timepoint. In addition, the changes in nasal examination result by treatment, visit and timepoint are presented with shift tables with total number of subjects, and number and percent of subjects who experienced a shift.

## **11 Interim analyses**

No interim analysis is planned.

## **12 Deviations from protocol analysis**

There are no deviations from the analyses planned in the protocol.

## **14 Tables, Listings and Figures**

The document with tables, figures and listings (TLF) shells presented in a separate document.

## Appendix 1     Markedly Abnormal Laboratory Safety Values, Vital Signs

**Table 1:     Markedly abnormal Criteria for Laboratory Tests**

HAEMATOLOGY				
Variable	Units	Age	Markedly Abnormal Criteria	
			Low	High
Hemoglobin	g/dL	6 mo-18 yr	≤ 8	NA
RBC	x10  /mm 	6 mo-18 yr	≤ 3.5	NA
Hematocrit	%	6 mo-18 yr	≤ 30	≥ 50
Leukocytes	x10  /mm 	6 mo to 18 yr	≤ 2.8	≥ 20
Neutrophils	x10  /mm 	6 mo-18 yr	≤ 1	≥ 10
Lymphocytes	x10  /mm 	2-18 yr	< 1	≥ 10
Eosinophils	%*	All ages	NA	≥ 10
Monocytes	%*	6 mo-18 yr	NA	≥ 15
Basophils	%*	6 mo-18 yr	NA	≥ 5
Platelets	x10  /mm 	6 mo-18 yr	≤ 50	≥ 750

\*The percentage indicates the *relative* number of each type of leucocytes in the blood. The *absolute* count is calculated by multiply the relative value (%) by the total leukocyte count/100.

HEMOSTASIS AND COAGULATION				
Variable	Units	Age	Markedly Abnormal Criteria	
			Low	High
Fibrinogen	g/L	All	NA	≥ 5
Prothrombin Time (PT)	seconds	All	NA	≥ 20
Partial Thromboplastin Time (APTT)	seconds	6 mo-18 yr	≤ 20	≥ 50

CHEMISTRY				
Variable	Units	Age	Markedly Abnormal Criteria	
			Low	High
ALT	U/L	1-19yr	Not applicable	$\geq 3x$ ULN
AST	U/L	10-19yr	Not applicable	$\geq 3x$ ULN
Total protein	g/L	> 1yr	$\leq 40$	$\geq 90$
Albumin	g/L	All	$\leq 25$	$> 60$
Alkaline phosphatase	U/L	All	Not applicable	$\geq 3x$ ULN
Total bilirubin	$\mu$ mol/L	10-18yr	Not applicable	$\geq 1.5x$ ULN
Creatinine	$\mu$ mol/L	All	Not applicable	$\geq 120$
Glucose	mmol/L	24m-11yr 12-18yr	$\leq 2.5$ $\leq 2.8$	$> 8$ $> 10$
GGT	U/L	All	Not applicable	$\geq 3x$ ULN
Urea nitrogen	mmol/L	All	Not applicable	$\geq 8.0$
Potassium	mmol/L	> 2m	$\leq 3$	$\geq 6$
Sodium	mmol/L	All	$\leq 130$	$\geq 150$
Calcium total	mmol/L	All	$\leq 1.8$	$\geq 3$
Chloride	mmol/L	All	$\leq 90$	$\geq 115$

**Table 2: Markedly abnormal Criteria for Vital Signs**

**Markedly abnormal Criteria for Pulse Rate**

Age	Low	High
9 years $\leq$ x < 11 years	$\leq 66$	$\geq 114$
11 years $\leq$ x < 13 years girls	$\leq 66$	$\geq 114$
11 years $\leq$ x < 13 years boys	$\leq 61$	$\geq 109$
13 years $\leq$ x < 15 years girls	$\leq 61$	$\geq 109$
13 years $\leq$ x < 15 years boys	$\leq 56$	$\geq 104$
15 years $\leq$ x < 17 years girls	$\leq 56$	$\geq 104$
15 years $\leq$ x < 17 years boys	$\leq 51$	$\geq 99$
17 years $\leq$ x < 19 years girls	$\leq 51$	$\geq 99$
17 years $\leq$ x < 19 years boys	$\leq 46$	$\geq 94$

**Markedly abnormal Respiratory rate (breaths/min)**

Age	Low	High
5 years $\leq$ x < 12 years	$\leq 10$	$\geq 40$
12 years $\leq$ x < 16 years	$\leq 7$	$\geq 40$
16 years $\leq$ x	$\leq 7$	$\geq 30$

**Markedly abnormal blood pressure levels for BOYS by age**

Age (years)	Unit	SBP Lower limit ( $\leq$ )	SBP Upper limit ( $\geq$ )	DBP Lower limit ( $\leq$ )	DBP Upper limit ( $\geq$ )
10 years $\leq$ x < 11 years	mmHg	77	127	34	88
11 years $\leq$ x < 12 years	mmHg	79	129	35	89
12 years $\leq$ x < 13 years	mmHg	81	131	35	89
13 years $\leq$ x < 14 years	mmHg	84	134	36	90
14 years $\leq$ x < 15 years	mmHg	86	136	36	90
15 years $\leq$ x < 16 years	mmHg	89	139	37	91
16 years $\leq$ x < 17 years	mmHg	92	141	39	93
17 years $\leq$ x < 18 years	mmHg	94	144	41	95
18 years $\leq$ x < 19 years	mmHg	94	144	41	95

**Markedly abnormal blood pressure levels for GIRLS by age**

Age (years)	Unit	SBP Lower limit (<math>\leq</math>)	SBP Upper limit (<math>\geq</math>)	DBP Lower limit (<math>\leq</math>)	DBP Upper limit (<math>\geq</math>)
10 years $\leq x < 11$ years	mmHg	78	126	35	86
11 years $\leq x < 12$ years	mmHg	80	128	36	87
12 years $\leq x < 13$ years	mmHg	81	130	37	88
13 years $\leq x < 14$ years	mmHg	83	132	38	89
14 years $\leq x < 15$ years	mmHg	85	134	39	90
15 years $\leq x < 16$ years	mmHg	86	135	40	91
16 years $\leq x < 17$ years	mmHg	87	136	41	92
17 years $\leq x < 18$ years	mmHg	87	136	41	92
18 years $\leq x < 19$ years	mmHg	87	136	41	92
